### **1. Background and Significance**

#### **Chronic musculoskeletal pain among older adults is prevalent and costly.**

Chronic musculoskeletal pain (pain >3 months) is common among older adults, with an estimated 60%–75% of older adults reporting at least some persistent pain. The incidence of chronic pain among older adults is expected to increase given the exponential growth in the older adult population over the next three decades and accompanying comorbidities. Estimated US health care costs of chronic pain range from \$261-300 billion, far exceeding the cost of diabetes, hypertension, heart disease, cancer, and other common chronic conditions. Among older adults, chronic pain leads to a significant decline in physical and emotional function with substantial disability from reduced mobility, avoidance of activity, falls, depression, anxiety, sleep impairment, and social isolation. Sedentarism, lack of engagement in activities of daily living, and impairments in balance and gait are common in older adults with chronic pain and further increase risk for morbidity and mortality.

#### **Older adults from underserved communities are at the highest risks for negative outcomes due to chronic pain.**

Older adults from underserved communities have disadvantaged backgrounds, low income, poor education, and tend to be racial and ethnic minorities and immigrants. Chronic pain is often poorly recognized, underestimated, and inadequately managed among these older adults. Disparities in chronic pain management are multidimensional, including gaps in patient/health care provider communication, variability in decision making, and gaps in access to effective treatment. Discrimination, systemic racism, stigma, social marginalization, lower education, and Medicaid insurance status are all associated with higher reports of pain intensity, higher psychological distress and disability among older adults with chronic pain.

#### **Management of chronic pain among older adults is inadequate, particularly for older adults from underserved communities.**

For older adults, pain medications including opioid analgesics have limited efficacy, increase risk for adverse events such as falls, and can lead to confusion and cognitive decline. Nonpharmacological treatments for chronic pain such as Cognitive Behavioral Therapy (CBT) or Mindfulness Based Interventions (MBIs) are safe for older adults and can improve pain outcomes including physical, and emotional function. However, treatment effects are small, decrease over time, and access to timely treatment is scarce. A recent systematic review published in JAMA highlighted the need for novel nonpharmacological treatments for chronic pain in older adults that can produce stronger and sustained effects.

Access to nonpharmacologic therapies is limited for many older adults from disadvantaged populations because therapies are not affordable, not recommended by providers, or not available in their community. For example, a recent study of specialty pain clinics found that close to half did not accept Medicaid and did not offer psychosocial treatment options. Our qualitative work also suggests that older adults with chronic pain are experiencing significant unrelieved pain and cannot easily access psychosocial interventions in their communities to better manage it.

**Group Visits (aka Shared Medical Appointments) may be a viable model to overcome many barriers experienced by older, underserved adults to high-quality chronic pain management.**

Group medical visits seek to improve patient health through a blend of medical care, education, and peer support. Previous research on group visits, which has included underserved community health centers and older adults, has demonstrated the feasibility, acceptability, and health benefits of group visits for patients with diabetes, cancer, and headaches. Group visits for older adults with chronic pain have substantial potential to overcome the challenges of patient stigma and insufficient clinician skills by: 1) creating a supportive community of patients who navigate pain together in a supportive clinical setting familiar to them with easy access to their clinical team; 2) providing evidence-based nonpharmacological pain treatment delivered by trained clinic staff; 3) efficiently integrating pain management into the routine flow of primary care; and 4) being financially feasible, scalable, and sustainable within primary care settings, as group medical visits can be reimbursed by Medicare, Medicaid and third party payers.

**The GetActive program is an evidence-based intervention developed by our team that is feasible and produces sustained moderate to large improvements in pain outcomes.**

GetActive was developed by our interdisciplinary team using the fear avoidance theoretical model (development and maintenance of pain occurs due to perception of pain as a threat and subsequent avoidance of activity), and guidelines from the International Classification of Functioning, Disability and Health (ICF) and the Initiative on Methods, Measurement and Pain Assessment in Clinical Trials (IMMPACT). GetActive combines “top down” CBT and MBI skills with walking, a “bottom up”, safe and preferred activity for older adults. GetActive directly targets improvement in all aspects of physical function delineated by IMMPACT: 1) self-report; 2) performance based/exercise capacity; and 3) objective (step-count). GetActive teaches: (1) *walking skills* based on behavioral/operant principles (e.g., how to gradually increase step-count by setting SMART (specific, measurable, attainable, realistic, time bound) goals; how to pair increases in walking with engagement in activities of daily living that are meaningful and valued;

how to apply pacing to safely break the connection between pain and activity; (2) *mind-body skills* to change one's relationship with pain (e.g., reduce reactivity, fear, ruminative self-talk -through relaxation response and mindfulness exercises) and to facilitate walking; (3) *pain, behavior awareness skills* to understand the disability spiral (e.g., how lack of activity perpetuates chronic pain and emotional and physical dysfunction); and (4) *positive psychology skills* to engage social support for walking; manage negative reactions from others and cope with stress or walking setbacks (positivity, self-compassion, and gratitude).

**The GetActive program can be tailored for the unique needs of disadvantaged, older adults and for routine integration in primary care clinics in underserved communities, as part of Group Medical Visits, with high potential for sustainability and scalability.**

[figure not shown]
While group visits for chronic pain have been initiated, they have not been developed specifically for older adults, and have not been rigorously tested in older adults or incorporated into routine care for older, disadvantaged adults. Community health centers (CHC) provide primary care for over 24 million patients in the United States, often in medically underserved and lower-income urban and rural communities. Because of the diversity of older patients seen by CHCs, they offer a unique and compelling opportunity to provide high quality psychosocial interventions for chronic pain and improve overall access to chronic pain management.

We partnered with the MGH-Revere HealthCare Center (RHC), which serves a diverse, underserved community, to integrate *GetActive+* into the group visit workflow of their practice to fit the need of their older patients, clinic staff and administration. RHC has a longstanding history of group visits for diabetes and obesity delivered by trained NPs, and will provide an optimal setting, infrastructure, and context for integrating *GetActive+* into a group visit framework. By developing, implementing, and evaluating this integrated model of *GetActive+* at RHC, we will set the stage for our long-term goal to implement and disseminate *GetActive+* in other community health centers in MA and nationally.

## 2. Specific Aims and Objectives

Conduct an open pilot trial (i.e., Aim 2 of P# 2022P001691) of the *GetActive+* program (i.e., a novel mind-body and activity program) followed by optional qualitative exit interviews with RHC patients (up to N=50). We will determine if the feasibility, acceptability, and fidelity of the program meet *a priori* benchmarks. We also hope to establish preliminary efficacy that the program improves physical function and other study outcomes we describe in sections below. We will use qualitative data to optimize the intervention and study procedures for future trials. See Figure 2 for aim 2 study schema.

Figure 2. Aim 2 Study Schema

\*Total number of patient participants (up to N=50)

### 3. General Description of Study Design

We will conduct an open pilot trial of the *GetActive+* program followed by individual qualitative exit interviews. We plan to conduct 3-6 groups of approximately 5-10 participants each (up to N=50). At least one of the 3-6 groups will be offered in Spanish and led by a fully trained Spanish speaking social worker and member of study staff. The goal of this phase will be to establish feasibility (primary), acceptability, and fidelity of the *GetActive+* program and study procedures. We will also explore improvements in study outcomes. We will recruit English and Spanish speaking older adults (55+) with chronic pain currently receiving medical care from RHC. Recruitment will be facilitated through posted IRB approved flyers, in-clinic approaches made by study staff, and referrals from RHC physicians, nurses, psychologists and other relevant staff (see section 4). These recruitment strategies are informed by recommendations from RHC staff and are supported by [REDACTED]. If patients indicate interest in participating, they will be guided through eligibility screening by study staff (see section 4). After screening, interested patients will discuss their availability for a baseline visit and the 10-week *GetActive+* program. A Research Assistant (RA) will keep track of potential participant preferences with regard to the days and times for intervention delivery and in person versus remote participation. The number of participants per group will vary based on availability, while typically ranging between 3 and 10. At the subsequent in person baseline assessment, patients will provide their informed consent in the presence of study staff and complete all assessments. They will also pick up their ActiGraph watch to wear for 7-10 days (see section 6). They will later return their ActiGraph either in person or in the mail via pre-paid envelop. These same procedures will be followed for Spanish speaking patients. All Spanish speaking patient interactions will be conducted by a native Spanish speaking RA. Additionally, all study materials have either already been translated and validated or will be translated into Spanish by a translation service or a native Spanish-speaking researcher.

The 10-week *GetActive+* program will be conducted either in-person or via Zoom and led by a fully trained member of study staff. Spanish speaking groups will follow the same structure and will be led by a fully trained native Spanish speaking member of study staff. In the event that group sessions are conducted virtually, we will use an MGB Zoom account. Zoom specifically states that their software is equipped to keep information secure, and the software does not have access to identifiable information. Zoom is HIPPA compliant, MGB approved, and the current video software standard for patient care within our Department of Psychiatry. Participants will be encouraged to attend as many group sessions as possible and complete their home practice assignments between sessions. Participants who can't attend the group sessions will be offered make-up sessions. Throughout these ten weeks, the RA will send participants daily reminders via text message to practice program skills, log home practice, and attend the sessions (contingent on their consent to receive such text messages). These text messages will be sent using Twilio, which will be integrated with our REDCap database. Participants will have the option to attend a 5-10 minute 1-on-1 medical check-in with the nurse practitioner before or after each group session. Within 3 days after the last group session, participants will complete the in person post-program assessments and pick up their ActiGraph to wear for the next 7-10 days (see section 6). They will return the ActiGraph in person or via a pre-paid envelope.

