## **5. Subject Enrollment**

Potential participants will be informed about the study through one of the methods described above (e.g., flyer, provider-including medical interpreters-referral, or via research assistant in the clinic). Participants will complete eligibility screening following any one of the procedures described in section 4. Only after having ample time to review the consent form will the RA

officially guide patients through written informed consent to take part in the research study. Patients who choose to provide their consent will do so electronically (i.e., REDCap eConsent) in the presence of the RA to ensure that all questions or concerns associated with participation are answered. The RA will track participants' preferences with regard to the days and times for intervention delivery and in-person versus Zoom participation. The number of people per group will vary based on participant availability with an expected range between 3 and 10 participants. Once a group is formed and no more than 2 weeks before the first group visit, the RA will schedule an in person visit to conduct informed consent and baseline assessments (see section 6). At this visit patients will receive an ActiGraph watch to wear for 7-10 days, and instructions on how to wear it.

All participants must be capable of understanding the nature of this study as well as the risks and potential benefits. All potential participants will have ample time and opportunity to ask questions or clarify concerns in person (if screened with research assistant) or over email or phone (if screened remotely over REDCap).

All stages of the study will be detailed, including the risks and benefits of the study. No information will be withheld from prospective or active participants regarding the study design. The participant will be reminded that they may decline to participate in this study, and they may discontinue study participation at any time. In this case, a participant will be asked their reason(s) for discontinuation, which may provide valuable feedback for improving future recruitment, retention, or study procedures.

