Adaptive coping	Self-Compassion Scale – Short Form (SCS-SF) ; assesses participants’ capacity for self-compassion. Pre, post  Gratitude Questionnaire (GQ-6) assesses individual differences in the proneness to experience gratitude in daily life. Pre, post  Applied Mindfulness Process Scale (AMPS) ; assesses how participants’ use mindfulness when facing challenges in daily life. Pre, post  Cognitive and Affective Mindfulness Scale – Revised (CAMS-R) ; measures mindfulness and the degree to which respondents’ experience thoughts and feelings. Pre, post  Measure of Current Status (MOCS) ; assesses current self-perceived status on the ability to relax at will, recognize stress-inducing situations, restructure maladaptive thoughts, be assertive about needs, and choose appropriate coping responses as needed. Pre, post

The *GetActive+* program will be conducted either virtually or in person (depending on patients’ preferences) by trained staff (psychologist or nurse practitioner, or both depending on availability) over the course of 10 weekly sessions. It is important that all eligible patients be able to participate should they choose to enroll. Thus, participants that wish to attend virtually but do not have the appropriate technology will be provided with a smart device, the type of which will be dependent on study funds and device availability. Prior to or directly after each session, participants will have the option to attend a 5-10 minute 1-on-1 medical check-in with the nurse practitioner. The purpose of these check-ins is to ensure that participants feel

physically safe and comfortable with the activity-based component of the program throughout the duration of their participation. Each of the 10 sessions will last approximately 60-minutes. Group sizes will be approximately 3-10 participants, however, this may be subject to change depending on the rate of attrition. Currently, we estimate approximately 20% attrition with the understanding that participant retention for this population might be less than what was observed in prior trials with *GetActive*. The interventionist will be trained by [name] and [name] and supervised weekly.

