All participants will wear ActiGraph devices to monitor activity levels for 7-10 days after their baseline assessment and post-intervention assessment. Following the baseline assessment period, participants will return the ActiGraph device either in person at their first group session or mail the device back to study staff if they will be attending group sessions virtually. The post-intervention assessments will be scheduled to take place approximately 3 days after the last group session (e.g., Session 10). Participants will receive their ActiGraph device and wear it for the following 7-10 days. Participants will return their ActiGraphs via pre-paid envelopes provided by study staff. Participants will also be given the option to share contact information with the other group members following the post-program assessments. This is an optional procedure for those interested in staying in touch following group sessions.

Only trained study staff will have access to the data collected at baseline and post-program. Participants' data will be identified by an ID number only, and a link between names and ID numbers will be password-protected and kept separately. The information on the ActiGraph accounts will be password protected and only the study staff and patient will have access to that information. Training sessions will be audio-recorded and reviewed to ensure fidelity. All group sessions will be audio-recorded. Recordings will be used for weekly clinical supervision (e.g., problem solve challenging cases), and to assess study therapist's competency and fidelity to the content of each session. All study staff will have up to date Collaborative Institutional Training Initiative (CITI) certifications. All study procedures will be conducted using our published methodology.

Following the conclusion of the program, patients will have the option to participate in an exit interview. These interviews will be conducted utilizing procedures outlined by Krueger and guided by a semi-structured IRB approved interview guide. The goal of these interviews will be to understand the experiences of participants and garner feedback on the program. This feedback will eventually be used to further optimize the *GetActive+* program for use in future studies. Participants will be able to choose whether they would like to attend the exit interview in person

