Participants will be compensated \$60 for completing the baseline visit and up to \$100 for the 7–10-day baseline ActiGraph assessment (e.g., \$10 per day up to 7-days; additional \$30 for 7 days of complete and valid data). Participants will also receive up to \$150 worth of travel compensation (e.g., if sessions are in person, \$15 per session for 10 sessions). If participants attend group sessions virtually, they will not be subject to the compensation associated with transportation. To incentivize long-term engagement with the program, participants will receive a \$50 bonus for attending at least 8 of the 10 sessions. Participants will also receive \$100 for the completion of the post-program assessments and up to \$155 for the post-program ActiGraph data collection period (e.g., \$15 per day up to 7-days; additional \$50 provided for 7 days of complete and valid data). In addition to all the above, participants will be given the opportunity to earn \$40 for attending an in-person post-program exit interview (\$25 for remote exit interviews). Select participants (based on randomization and interest) can also receive \$40 for an additional focus group. Payments will be submitted and sent to participants following each major time point (i.e., baseline, final group session, and post-program exit interview). Overall, participants of the open pilot will earn up to \$695.

All study procedures for Spanish speaking groups will be identical to English groups. Participant interactions will be in Spanish through a native Spanish speaking RA and group facilitator (i.e., a native Spanish-speaking social worker). Spanish speaking study staff will be fully trained in the

GetActive+ intervention and study procedures. All study materials are translated and spot check by a Spanish speaking RA.

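### The post-program assessment is described only as an in-person visit, with no remote route for the questionnaires, so the secondary pre-post results risk resting on completers alone

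*Combined protocol and SAP*

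**What the plan says.** Section 3 gives both mode and timing of the post-program assessment: "Within 3 days after the last group session, participants will complete the in person post-program assessments and pick up their ActiGraph". Section 6 restates the timing and is silent on mode: "The post-intervention assessments will be scheduled to take place approximately 3 days after the last group session (e.g., Session 10").

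Section 5 describes leaving the study: "they may discontinue study participation at any time. In this case, a participant will be asked their reason(s) for discontinuation". It does not mention people who stop going to sessions but remain in the study. Section 6 expects losses: "Currently, we estimate approximately 20% attrition with the understanding that participant retention for this population might be less than what was observed in prior trials". Section 3 sets the size: "We plan to conduct 3-6 groups of approximately 5-10 participants each (up to N=50").

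Section 9 compares pre and post values by paired t-test or Wilcoxon signed rank test and gives no rule for a missing post value.

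Remote methods are used elsewhere: phone screening (section 4), Zoom sessions and text messaging linked to REDCap (section 3), and, in section 6, texted links to home practice surveys, loaned devices for virtual attenders who lack one, and ActiGraph return by pre-paid envelope. The exit interview can also be remote: "Participants will be able to choose whether they would like to attend the exit interview in person", and the sentence goes on to offer Zoom.

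**The concern.** Both paired tests need a baseline and a post value from the same person. If the post value can be obtained only at one visit, a missed visit removes that person from every comparison that depends on it: the self-report measures (physical function, depression, anxiety, pain and coping among them), the 6-minute walk, and step count, because the device is handed out there. Of these, only the walk clearly needs the person to be present.

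A participant who attended all sessions by Zoom and cannot travel when the visit falls due has no described way to complete even the questionnaires. Nor does the plan tell a site to approach someone who has stopped attending, so practice could differ across the 3 to 6 groups.

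The stake is the preliminary efficacy signal. Sections 2 and 9 intend to report it, and section 8 says the pilot will prepare the R33 phase. If people who miss the visit changed less than those who attend, the reported effect sizes would be too large for the enrolled cohort. Without their data, this cannot be checked.

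**Working it through.** The plan gives no power calculation, alpha or effect-size assumption, so there is no stated figure to reproduce.

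**Which data depend on the visit**

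| Data | Needs the post visit as written? |
|---|---|
| Feasibility: agreement to participate | No |
| Acceptability: session completion among those enrolled | No |
| Fidelity: rated session components | No |
| Quota-based pacing questionnaire (weekly) | No |
| Clinical data taken from chart review | No |
| Post self-report measures | Yes, but could be done remotely |
| Post step count (ActiGraph) | Yes, but the device could be mailed |
| Post 6-minute walk | Yes |

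**Number of pairs**

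Inputs: N = 50, the section 3 maximum, and attrition a = 0.20 from section 6. Assumption: everyone counted as attrition lacks post data.

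Pairs = N × (1 − a) = 50 × 0.80 = 40. At an assumed a of 0.10 there are 45, and at 0.30 there are 35.

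**Power**

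This uses the noncentral t for a paired t-test, with two-sided alpha 0.05 and d = 0.5 (both assumed). Power is 0.93 with 50 pairs and 0.87 with 40. With N = 30 it falls from 0.75 (30 pairs) to 0.65 (24 pairs). At the full sample size the loss of precision is modest, so selection matters more.

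**Selection**

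Change over all enrolled = (1 − a) × completer change + a × leaver change, in the same SD units. With a = 0.20 and an assumed completer change of 0.50, the medium cut-off in section 9:

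- Leavers unchanged: 0.80 × 0.50 + 0.20 × 0 = 0.40.
- Leavers worse by 0.50: 0.80 × 0.50 + 0.20 × (−0.50) = 0.30.
- Leavers improved equally: 0.80 × 0.50 + 0.20 × 0.50 = 0.50, so no bias.

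At an assumed a of 0.30 with leavers unchanged: 0.70 × 0.50 = 0.35.

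**The case against.** The strongest reply is that the plan's main purpose is untouched. The primary outcomes are feasibility, acceptability and fidelity, and people who stop attending still count in the acceptability denominator. A reader might infer that non-attenders disappear from every outcome; the table above shows otherwise. There is also no efficacy go/no-go benchmark, so a shift from 0.50 to 0.40 changes no stated decision. This stands, and it limits the point to the secondary pre-post outcomes.

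A reader might also infer that people who stop sessions are barred from the visit. No text says so. Section 6 anchors timing to Session 10, a group date; the $100 for post-program assessments is separate from the $50 attendance bonus; and make-up sessions are offered. Inviting non-attenders is therefore mostly a clarification. Likewise, section 6 gives an approximate time, and nothing says a late visit is refused.

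Travel payment is not evidence that Zoom participants are disadvantaged at this visit. Section 6 says "If participants attend group sessions virtually, they will not be subject to the compensation associated with transportation", but that payment is per group session, and no travel payment is stated for anyone's post visit. Everyone has also attended baseline in person.

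Nor would the Patient Global Impression of Change, collected only at post, lack all unfavourable answers: attenders who did not improve also complete it.

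Finally, remote completion differs from baseline, where the research assistant supervises and helps. This is a real cost, but a smaller one than having no post value. None of these replies supplies a route for someone who does not come in.

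**Conclusion.** The concern holds for the secondary pre-post outcomes. The plan states an in-person assessment, gives no alternative for the self-report measures or for delivering the ActiGraph, and uses tests that drop unpaired participants, while already running the platforms that would avoid much of the loss.

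The size is illustrative. Section 6 states its 20% when discussing group size and does not say that those people will lack post data, so 40 of 50 is an assumption. So are the completer and leaver changes. A reader might conclude that the reported effect will be inflated; the documents support only that it could be, by 0.10 SD in the central illustration and by nothing if leavers changed equally. The plan as written would not show which applies. This is an inexpensive improvement to a pilot, not a flaw in its primary benchmarks.

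**What to change.** In sections 3 and 6:

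- State that every enrolled participant who has not withdrawn consent is invited to the post-program assessment, timed from their group's Session 10 whatever their own attendance.
- Keep the in-person visit as the default. For anyone who will not or cannot come in, collect the self-report measures by REDCap link or phone and mail the ActiGraph with a pre-paid return envelope, omitting only the 6-minute walk.
- Record the mode of completion for each participant, and report post-assessment completion by attendance.
- Align the two timing statements: section 3 sets a limit of 3 days, and section 6 gives approximately 3 days.

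The cost is protocol wording, a survey link on an existing platform, staff time for calls and a small outbound mailing cost, since the envelope is now described only for returns. Some post questionnaires will be completed in a different, less supervised mode from baseline; recording the mode lets this be examined. The change cannot recover people who withdraw consent or do not respond, so 50 pairs is an upper bound.
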